#### 5.2. General Methods

Unless otherwise explicitly stated, descriptive statistics for continuous variables are n, mean, median, standard deviation, minimum, and maximum. Descriptive statistics for categorical variables are the percentage (%) and the numerator (n) and the denominator (N) used in the percentage calculation.

##### 5.2.1. Analyses for Binary Data

The exact CI (Clopper-Pearson CI) for a single proportion of an individual group will be computed using the F distribution. If r is the number of responses and n is the number of subjects, then it follows that  $p=r/n$  is the estimate of the proportion of responses. An exact 95% CI can be computed by solving the following 2 equations. For the lower limit  $P_L$ ,

$$P_L = \frac{rF_L}{(rF_L + (n - r + 1))}$$

and for the upper limit  $P_u$ ,

$$P_u = \frac{(r + 1)F_u}{(n - r) + (r + 1)F_u}$$

where  $F_L$  is the quantile from the F distribution for  $\alpha=0.025$ , with numerator degrees of freedom equal to  $2r$  and denominator degrees of freedom equal to  $2(n-r+1)$ .  $F_U$  is the quantile from the F distribution for  $\alpha=0.975$ , with numerator degrees of freedom equal to  $2(r+1)$  and denominator degrees of freedom equal to  $2(n-r)$ . When  $r$  equals 0,  $F_L$  should be set equal to 1.0 so  $P_L$  equals 0. When  $r$  equals  $n$ ,  $F_U$  should be set equal to 1.0 so  $P_U$  equals 1.0.

The CI using the F distribution is described in [Collett \(1991\)](#) and implemented in SAS PROC FREQ.

Similarly, for the safety results, the exact 2-sided 95% CIs will be provided by vaccine group for all primary safety endpoints, ie, proportions of subjects reporting local reactions, systemic events, and AEs.

The 2-sided 95% CI on MDV minus PFS will be compiled using the method of [Chan and Zhang \(1999\)](#), but only for tier 1 and tier 2 events.

### 5.2.2. Analyses for Continuous Data

For each vaccine group, the GMCs and GMTs and the associated 95% CIs at 1 month after the infant series and 1 month after the toddler dose will be provided. The GMC or GMT will be calculated as the mean of the assay results after making the logarithmic transformation and then back transformation to the antilog scale. Two-sided 95% CIs will be constructed by back transformation of the CI for the mean of the logarithmically transformed assay results computed based on the Student t distribution.

For the GMCs, 2-sided 95% CIs for the ratio of 2 geometric means (MDS divided by PFS) will be compiled by back transformation of the CIs for the mean difference of the 2 logarithmically transformed assay results computed using the Student t distribution. The mean difference of the logarithmically transformed results is equivalent to the mean of the ratio on the logarithmic scale:  $\log(x/y) = (\log x) - (\log y)$ .

Similarly, for the GMTs, 2-sided 95% CIs for the ratio of 2 geometric means (MDS divided by PFS) will be constructed.

Reverse cumulative distribution curves (RCDCs) will be presented graphically by vaccine group (MDV, PFS) for each serotype-specific pneumococcal IgG antibody concentration and OPA titer after the infant series and after the toddler dose.

## 5.3. Methods to Manage Missing Data

### 5.3.1. Immunogenicity Data

The LLOQs by serotype for Pfizer's Luminex-based immunoassay were set as shown in [Table 8](#).

**Table 8. LLOQs for the Luminex-Based Immunoassay**

Serotype	LLOQ (µg/mL)
1	0.002
3	0.004
4	0.005
5	0.002
6A	0.005
6B	0.015
7F	0.003
9V	0.013
14	0.005
18C	0.002
19A	0.038
19F	0.012
23F	0.009

Abbreviation: LLOQ = lower limit of quantitation.

The OPA LLOQ titer for each serotype is as follows: 1, 18; 3, 12; 4, 21; 5, 29; 6A, 37; 6B, 43; 7F, 113; 9V, 141; 14, 35; 18C, 31; 19A, 18; 19F, 48; and 23F, 13.

Any antibody concentration or antibody titer below the LLOQ will be assigned to the lower limit of detection (LOD), defined as  $0.5 \times \text{LLOQ}$ . No other assay data will be imputed in the analyses. All immunogenicity analyses will be performed after the imputation of the antibody concentrations or antibody titers that are below the LLOQ.

### 5.3.2. Safety Data

Handling of missing information related to safety data, such as a missing or partially missing date, will be in accordance with Pfizer reporting standards.

For derived variables in reactogenicity data, if any day of the 7-day e-diary is available, the “Day 1 to Day 7” data will be considered to be nonmissing for analysis after each dose. The proportion of subjects with missing reactogenicity data will also be summarized by each dose in the infant series and the toddler dose for each vaccine group. The denominator will be the number of subjects who receive the scheduled vaccination.

## 6. ANALYSES AND SUMMARIES

### 6.1. Primary Endpoint(s)

**Endpoints:** Safety endpoints in [Section 3.1](#).

- Analysis intervals:

Endpoints for local reactions and systemic events: 7 days after each dose of the infant series and the toddler dose.

Endpoints for AEs: from the first dose up to 1 month after the infant series. Also from the toddler dose up to 1 month after the toddler dose.

Endpoints for SAEs: from the first dose up to 1 month after the toddler dose.

Endpoint for newly diagnosed chronic medical conditions: from 1 month after the infant series up to the toddler dose.

- Analysis population: Infant or toddler safety population, as relevant. SAE analysis will include subjects in either the infant or toddler safety population.
- Analysis methodology: Descriptive.
- Supporting objective: Primary objective.

### Reporting Results:

The number, proportion, and corresponding 95% CI will be presented for each vaccine group for each infant dose and the toddler dose.

Local reactions and systemic events that persist beyond Day 7 will be listed.

### 6.2. Secondary Endpoints

**Endpoints:** Immunogenicity endpoints in [Section 3.2](#).

**Endpoint:** The proportion of subjects with IgG concentration equal to or above the defined threshold for each of the pneumococcal serotypes measured.

- Analysis time points: 1 Month after the infant series and 1 month after the toddler dose.
- Analysis populations: Evaluable immunogenicity populations (infant and toddler) and all-available immunogenicity populations (infant and toddler).
- Analysis methodology: Descriptive.
- Supporting objective: Secondary objective.

### **Reporting Results:**

The numerator and denominator used for percentage, the percentage, and associated 95% CI will be presented for each vaccine group for the infant series and the toddler dose. The differences (MDV minus PFS) in percentage and corresponding CIs for the infant series and the toddler dose will also be presented.

**Endpoint:** The serotype-specific IgG GMC for each of the pneumococcal serotypes measured.

- Analysis time points: 1 Month after the infant series and 1 month after the toddler dose.
- Analysis population: Evaluable immunogenicity populations and all-available immunogenicity populations.
- Analysis methodology: Descriptive.
- Supporting objective: Secondary objective.

### **Reporting Results:**

The number of subjects, GMC, and associated 95% CI will be presented for each vaccine group for the infant series and the toddler dose. The geometric mean ratios (MDV divided by PFS) and corresponding CIs will also be presented.

**Endpoint:** The serotype-specific OPA GMT for each of the pneumococcal serotypes measured.

- Analysis time points: 1 Month after the infant series and 1 month after the toddler dose.
- Analysis populations: Evaluable immunogenicity populations and all-available immunogenicity populations.
- Analysis methodology: Descriptive.
- Supporting objective: Secondary objective.

### **Reporting Results:**

The number of subjects, GMT, and associated 95% CI will be presented for each vaccine group for the infant series and the toddler dose. The geometric mean ratios (MDV divided by PFS) and corresponding CIs will also be presented.

**Endpoint:** The proportion of subjects achieving a serotype-specific OPA titer  $\geq$  LLOQ for each of the pneumococcal serotypes measured.

- Analysis time points: 1 Month after the infant series and 1 month after the toddler dose.
- Analysis populations: Evaluable immunogenicity populations and all-available immunogenicity populations.
- Analysis methodology: Descriptive.
- Supporting objective: Secondary objective.

### **Reporting Results:**

The numerator and denominator used for percentage, the percentage, and associated 95% CI will be presented for each vaccine group for the infant series and the toddler dose. The differences (MDV minus PFS) and corresponding CIs will also be presented for both the infant series and the toddler dose.

AEs occurring prior to the first vaccination will be excluded from AE analysis, unless the severity increases after dosing. AEs occurring between the informed consent document signoff and prior to the first vaccination will be summarized separately.

Any AE that starts in the infant series and continues past the toddler dose will be assigned only in the infant series.

For tier 1 and tier 2 events, the proportion of AEs observed in each vaccine group will be presented along with the point estimates and associated 95% CIs of the risk difference (the difference of incidence rates) between MDV and PFS. The 95% CIs will be calculated using the Chan and Zhang method described in [Section 5.2.1](#).

For tier 1 events, p-values from Chan and Zhang's method will be calculated and included in the presentations. AEs will be arranged in the output sorted in descending order of point estimates of the risk difference (the difference of incidence rates) within system organ class.

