4.1. Inclusion Criteria

Subjects must meet all of the following inclusion criteria to be eligible for enrollment into the study:

1. Evidence of a personally signed and dated informed consent document indicating that the parent(s)/legal guardian(s) has/have been informed of all pertinent aspects of the study.
2. Parent(s)/legal guardian(s)/caregiver(s) willing and able to comply with scheduled visits, treatment plan, and other study procedures.
3. Aged 6 weeks (42 to 72 days) at the time of vaccination. (The day of birth is considered Day 0.)
4. Available for the entire study period and whose parent(s)/legal guardian(s)/caregiver(s) can be reached by telephone.
5. Healthy infant as determined by medical history, physical examination, and judgment of the investigator.
6. Weight of 3.0 kg or greater at the time of vaccination.

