6.1.3. Toddler Dose (12 Months of Age)

6.1.3.1. Visit 5 (365 to 420 Days of Age)

- Based on clinical evaluation, determine whether SAEs or newly diagnosed chronic medical conditions have occurred since the last study visit and record them on the CRF.
- Review AEs that were ongoing from the previous visit and record their end dates or confirm that they are still ongoing.
- On the day of vaccination, prior to vaccination, measure and record the subject's axillary temperature.
- Ensure that the subject continues to be eligible for the study and meets none of the withdrawal criteria ([Section 6.2](#)).
- Ensure that the subject does not meet any of the temporary delay criteria ([Section 4.3](#)).

- An appropriate site staff member will use the IRT system to obtain the subject's investigational product DU or container number.
- Administer a single 0.5-mL intramuscular injection of 13vPnC from an MDV or a PFS into the anterolateral thigh muscle of the left leg.
- Administer a single dose of hepatitis A virus vaccine into a different limb from that used to administer 13vPnC, according to local clinical practice.
- Observe the subject for at least 30 minutes after vaccination for any significant acute reactions. Any AE noted during the observation period should be recorded on the source documents and on the AE section of the CRF.
- Issue a caliper and a digital thermometer to the parent(s)/legal guardian(s)/caregiver(s) and provide instructions on their use.
- Issue a subject e-diary to the parent(s)/legal guardian(s)/caregiver(s). Provide instruction on its completion for 7 days (Day 1 through Day 7, where Day 1 is the day of vaccination).
- Ask the parent(s)/legal guardian(s)/caregiver(s) to contact the investigator immediately if any significant illness or hospitalization occurs during the study period, or if the subject experiences a large (>14 caliper units) local reaction.
- Schedule an appointment with the parent(s)/legal guardian(s)/caregiver(s) for the next study visit.
- Remind the parent(s)/legal guardian(s)/caregiver(s) to bring the e-diary to the next study visit.
- The investigator or an authorized designee completes the source documents, completes the CRF, and updates the investigational product accountability records.

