8.2. Definitions

8.2.1. Adverse Events

An AE is any untoward medical occurrence in a study subject administered a product or medical device; the event need not necessarily have a causal relationship with the treatment or usage. Examples of AEs include, but are not limited to:

- Abnormal test findings;
- Clinically significant signs and symptoms;
- Changes in physical examination findings;

- Hypersensitivity;
- Progression/worsening of underlying disease;
- Drug abuse;
- Drug dependency.

Additionally, AEs may include signs and symptoms resulting from:

- Drug overdose;
- Drug withdrawal;
- Drug misuse;
- Drug interactions;
- Extravasation;
- Exposure during pregnancy (EDP);
- Exposure via breastfeeding;
- Medication error;
- Occupational exposure.

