8.3. Severity Assessment

GRADE	If required on the AE page of the CRF, the investigator will use the adjectives MILD, MODERATE, SEVERE, or LIFE-THREATENING to describe the maximum intensity of the AE. For purposes of consistency, these intensity grades are defined as follows:	
1	MILD	Does not interfere with subject's usual function.
2	MODERATE	Interferes to some extent with subject's usual function.
3	SEVERE	Interferes significantly with subject's usual function.
4	LIFE-THREATENING	Life-threatening consequences; urgent intervention indicated.

Note the distinction between the severity and the seriousness of an AE. A severe event is not necessarily an SAE. For example, a headache may be severe (interferes significantly with the subject's usual function) but would not be classified as serious unless it met one of the criteria for SAEs, listed above.

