9.1. Sample Size Determination

Sample size is justified by the probability of detection of AEs and the precision of estimates of GMCs. The sample size of 150 per group offers reasonable detection probability of AEs commonly seen in other studies, and provides reasonable width of the confidence interval (CI) around the GMC.

The primary endpoints include the incidence of AEs in the MDV group. AE incidences were obtained from infant series data from a related Pfizer study, B4671001. The incidences from the 2 vaccine groups, MDV and PFS, were combined. The combined sample size was 500. The probability of detecting at least 1 indicated event is presented in Table 5. Incidences are sorted in descending order.

Table 5. Probability of Detection of at Least 1 Adverse Event in the Infant Series

	Incidence After Combining MDV and PFS (n=500 in Study B4671001)	Proposed Sample Size for MDV in Study B4671004	Probability of at Least 1 Indicated AE
Any AE	50.0%	150	100.0%
Any related AE	0.6%	150	59.5%
Any SAE	0.2%	150	25.9%

Abbreviations: MDV = multidose vial; PFS = prefilled syringe.

For the immunogenicity comparison of the MDV and PFS groups, 2-sided 95% CIs comparing the groups will be compiled, but no formal noninferiority criteria are specified.

Precision for GMCs is quantified by dividing the upper limit of the 95% CI by the GMC. Standard deviations (SDs) of each serotype's assays, in log scale, were derived from Table 21 in the B4671001 clinical study report (CSR). Assay SDs were obtained for both MDV and PFS intervals. CCI

[REDACTED]

CCI [REDACTED]

CCI

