### 3. ENDPOINTS AND BASELINE VARIABLES: DEFINITIONS AND CONVENTIONS

#### 3.1. Primary Endpoints

- Incidence of local reactions and systemic events at the following time periods in the MDV group and in the PFS group:
  - Within the 7 days after the first dose of the infant series.
  - Within the 7 days after the second dose of the infant series.
  - Within the 7 days after the third dose of the infant series.
  - Within the 7 days after the toddler dose.
- Incidence of adverse events (AEs) in the MDV group and in the PFS group from the first dose up to 1 month after the infant series.
- Incidence of AEs in the MDV group and in the PFS group from the toddler dose up to 1 month after the toddler dose.
- Incidence of serious adverse events (SAEs) in the MDV group and in the PFS group from the first dose up to 1 month after the toddler dose.
- Incidence of newly diagnosed chronic medical conditions in the MDV group and in the PFS group from 1 month after the infant series up to the toddler dose.

Each day of vaccination will be considered Day 1.

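### An infant-series AE kept as one record that worsens after the toddler dose is not attributed to the toddler-dose AE endpoint, although the first-dose rule counts such worsening

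*SAP*

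**What the plan says.** The AE counting rules stand at the end of SAP Section 6.2, after the last immunogenicity endpoint. Two of them deal with an event that is already present when a dose is given.

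- First dose: "AEs occurring prior to the first vaccination will be excluded from AE analysis, unless the severity increases after dosing".
- Toddler dose: "Any AE that starts in the infant series and continues past the toddler dose will be assigned only in the infant series".

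The endpoint affected is listed in SAP Section 3.1: "Incidence of AEs in the MDV group and in the PFS group from the toddler dose up to 1 month after the toddler dose". SAP Section 4.3 gives the toddler dose its own safety population, and SAP Section 6.1 gives it its own analysis interval.

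Three protocol provisions decide what data will exist. Section 8.2.1 includes "Progression/worsening of underlying disease" among its examples of AEs. Section 6.1.3.1 (Visit 5) instructs the site: "Review AEs that were ongoing from the previous visit and record their end dates or confirm that they are still ongoing". Section 6.1.4.1 (Visit 6) gives the same instruction. Section 8.3 says that the grade, where the CRF asks for one, is used "to describe the maximum intensity of the AE".

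**The concern.** The two rules treat similar situations differently. A condition present before Dose 1 that gets worse after Dose 1 enters the AE analysis. A condition that began in the infant series and gets worse after Dose 4 stays with the infant series, an interval that closed months before the worsening. Neither document gives a reason for the difference.

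The study exists to describe safety, and AE incidence in the month after the toddler dose is one of its primary endpoints. Worsening of a persisting condition soon after a vaccination is something a reader would expect that endpoint to show. Under the present wording, a child whose only event in the interval is such a worsening, held on the original record, appears in the toddler table as having had no AE.

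**Working it through.** **Inputs.** Group size: "The sample size of 150 per group offers reasonable detection probability of AEs commonly seen in other studies" (Protocol Section 9.1). Age at Dose 1: "Aged 6 weeks (42 to 72 days) at the time of vaccination" (Protocol Section 4.1). Visits 2, 3 and 4 each fall 28 to 42 days after the visit before, and Visit 5 falls at 365 to 420 days of age (Protocol Sections 6.1.1.2 to 6.1.3.1).

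**1. The plan's own figure.** Protocol Table 5 gives the probability of at least one event among 150 children, 1 − (1 − p)^150:

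- p = 50.0%: 100.0%
- p = 0.6%: 1 − 0.994^150 = 59.5%
- p = 0.2%: 1 − 0.998^150 = 25.9%

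All three match. This point disputes no stated figure; the check only confirms the group size.

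**2. Tracing one event.** Suppose a mild AE starts after Dose 2 and is still present at Visit 5.

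- At Visit 5 the site confirms it as ongoing. No instruction asks for a new record if it later worsens.
- After Dose 4 it becomes moderate. On a single record, the grade becomes the new maximum and the start date stays in the infant series. Neither document provides for a date of severity change.
- The SAP rule then assigns the AE to the infant series only. The toddler-dose count for this event is zero.

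Had the same event begun before Dose 1 and worsened after it, the first-dose rule would have counted it. No other section of either document brings the toddler-dose worsening back into the toddler interval.

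**3. How long such an event must last.**

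- Age at Visit 4: earliest 42 + 3 × 28 = 126 days; latest 72 + 3 × 42 = 198 days.
- Gap from Visit 4 to Visit 5: shortest 365 − 198 = 167 days; longest 420 − 126 = 294 days.

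An AE that began by Visit 4 must therefore persist for at least 167 days to be ongoing at the toddler dose. This uses the nominal windows, which the protocol accepts may not always be kept.

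**4. Size per child.**

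- One child in 150: 1/150 = 0.67 percentage points on that group's any-AE incidence, provided the child has no other AE in the interval. The figure is slightly larger if fewer than 150 children receive the toddler dose.
- For scale, the only all-cause AE rate in the documents is the 50.0% in Table 5, which is from the infant series of an earlier study. At that rate the 95% half-width is about 1.96 × √(0.5 × 0.5/150) = 8.0 points.
- For a single AE term, exact (Clopper-Pearson) 95% limits are 0 to 2.4% for 0/150 and 0.02% to 3.7% for 1/150.
- The documents give no rate of affected children. Purely as an assumption, 0.2% to 2% of 150 would be 0.3 to 3 children per group. The conclusion does not depend on this range.

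**The case against.** The strongest reply is that the two rules do different jobs. The first-dose rule decides whether an event enters the AE analysis at all; without its exception a worsened pre-dose event would vanish. The toddler rule allocates an event that is already counted to one of two intervals. That is fair. A reader might infer that the SAP contradicts itself, and it does not. What stands is that the allocation places worsening after Dose 4 in an interval that ended before it happened.

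A reader might also infer that such worsening can never count in the toddler interval. The documents do not support that. Protocol Section 8.2.1 allows worsening of an underlying disease to be an AE, and AEs are actively collected from Visit 5 to Visit 6 (Section 8.1.4). A site that opened a new record would give it a start date after the toddler dose, and the SAP rule would not reach it. But this is left to the site, so handling may differ between sites.

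Nor is the event discarded. It remains in the infant-series AE incidence, itself a primary endpoint. If serious, it also falls in the SAE interval running from the first dose to one month after the toddler dose (SAP Section 6.1).

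Finally, the children are enrolled as healthy, serious chronic disorders are excluded, and the event must both last at least 167 days and then worsen within about a month of the dose. Few will qualify. This stands in full.

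**Conclusion.** The point holds as a narrow gap in attribution. For an AE that starts in the infant series, is kept as one continuing record and becomes more severe after the toddler dose, the SAP assigns the whole event to the infant series, and the toddler-dose primary endpoint does not reflect the worsening.

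The effect is an understatement of about 0.67 points in a group's any-AE incidence for each affected child with no other AE in that interval, assuming a denominator of 150. How many children this concerns cannot be derived from the documents, and it is probably very few. It might be tempting to read the rule as biasing the comparison of MDV with PFS. The documents do not support that: the rule is identical in both randomized groups, and the study is descriptive with no decision rule (SAP Section 5.1). This is a cheap improvement and does not threaten the study's conclusions.

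**What to change.** Two changes, made together.

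- **SAP Section 6.2.** Extend the toddler rule with the exception already used for the first dose: the AE stays with the infant series unless its severity increases after the toddler dose, in which case it is also counted in the toddler-dose interval.
- **CRF completion instructions.** Ask sites to record such worsening as an AE with its own start date. Without this the SAP clause cannot be programmed reliably, because the severity field holds only the maximum grade and carries no date. With it, recording no longer depends on each site's habit, and the SAP clause makes the intended counting explicit.

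If the sponsor means the toddler rule to be stricter, a sentence giving the reason would serve instead.

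The cost is one SAP clause, one CRF completion note, and a footnote that a worsened event may appear in both the infant-series and toddler-dose tables. Within each endpoint a child still counts at most once.
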